8. HANDLING OF MISSING DATA

For the analyses of efficacy endpoints, subjects who have a missing value at the TOC visit or FU visit will be assigned as treatment failures, i.e., non-responders or positive mycological outcome.

The handling of below level of quantitation (BLQ) values in PK analysis will be described in the section below.

No other imputation will be used unless otherwise specified.

9. INTERIM ANALYSIS

No interim analysis is planned for this study.

10. DATA CONVENTIONS FOR ANALYSIS

10.1 General Statistical Principles

All statistical tests will be performed at the unadjusted 0.05 (two-sided) or equivalently 0.025 (one-sided) level of significance. The study is not powered for formal statistical comparisons.

All observed and derived variables (e.g., change from baseline, response status) used in the summaries of analyses will be presented in by-subject listings. Descriptive statistics will be used to provide an overview of the efficacy and safety results. For categorical parameters, the number and percentage of subjects in each category will be presented. The denominator for percentage will be based on the number of subjects appropriate for the purpose of analysis. For continuous parameters, descriptive statistics will include number of subjects, mean, standard deviation (SD), median, minimum, and maximum.

10.2 Study Day

Day 1 is defined as the date of first study drug administration. Study day is calculated relative to the date of Day 1.

10.3 Baseline and Change from Baseline

Baseline is defined as the last non-missing assessment prior to the date (and time if appropriate) of the first dose of study drug. Change from baseline is defined as: post-baseline value – baseline value.

10.4 Analysis Visit Window

Wherever applicable, efficacy and safety endpoints at Visit 1/ Screening, Visit 2/ Baseline, Visit 3/ Day 3, and Visit 5/ FU/ Day 25 will be analyzed according to their nominal visits. Visit 4/ TOC/ Day 10 will be analyzed according to the analysis window of study day 8 to study day 13, inclusive. Unscheduled visits from subjects who attended the TOC visit late will be included if within the analysis window. The bounds may be revised after reviewing blinded data. If more than one evaluation is assigned to this window, the evaluation closed to study day 10 will be used for the analysis. If the two visits are equidistant from the target day, the earlier visit will be used. Unscheduled visit assessments will be displayed in by-subject listings, without being included in the summaries.

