14.7 Safety Laboratory Tests

Safety laboratory tests will be performed by a qualified central laboratory. Safety laboratory tests will also be performed at the Screening, TOC visit and at unscheduled visits, if needed. If indicated, these may be done more frequently as follow up to a laboratory abnormality.

The following laboratory parameters will be determined:

Hematology

- White blood cell (WBC) count
- Red blood cell (RBC) count
- Platelet count
- Hemoglobin
- Hematocrit
- Differential WBC count will include percentages for lymphocytes, monocytes, eosinophils and basophils, and absolute counts for neutrophils, lymphocytes, atypical lymphocytes, monocytes, eosinophils and basophils.

Blood Chemistry

- Glucose
- Albumin
- Sodium
- Potassium
- Alkaline Phosphatase
- Creatinine
- Total creatine phosphokinase (CPK)
- Aspartate aminotransferase (AST/SGOT)
- Alanine aminotransferase (ALT/SGPT)
- Gamma glutamyl transferase (GGT)
- Bilirubin (total, direct and indirect)
- Total protein

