16.3 Events of Clinical Interest

The following are considered events of clinical interest (ECIs) if they occur after dosing, and must be reported by the site when it becomes aware of the ECI:

- ALT or AST > 8 x the upper limit of normal (ULN), confirmed by repeat testing
- ALT or AST > 5 x ULN for more than 2 weeks if new compared to Baseline, confirmed by repeat testing
- ALT or AST > 3 x ULN **and** either total bilirubin >2 x ULN or international normalized ratio (INR) >1.5 if new compared to Baseline, confirmed by repeat testing
- ALT or AST > 3 x ULN, confirmed by repeat test, with the appearance of fatigue, nausea, vomiting, right upper quadrant pain or tenderness, fever, rash, and/or eosinophilia (> 5%)

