11.10.2 Clinical Laboratory Testing

Absolute values and changes from baseline will be summarized for clinical laboratory (chemistry and hematology) results using descriptive statistics. Shift tables for each clinical laboratory test will cross-tabulate the number of subjects with values below the laboratory reference range (low), values within the laboratory reference range (normal) or above the laboratory range (high)

at baseline with the number of subjects with low, normal or high values at each post-baseline time point. Normal ranges and values outside the normal ranges will be identified by the central laboratory. A separate listing of out of normal range laboratory results will be provided.

Urine pregnancy test will be presented with subject childbearing potential in a by-subject listing.

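### The SAP's lab summaries leave out most unscheduled results and have no ULN-multiple categories, so they cannot show a repeat-confirmed hepatic event of clinical interest by arm

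*SAP*

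**What the plan says.** **Events.** Protocol 16.3 defines four hepatic events of clinical interest, the first being "ALT or AST > 8 x the upper limit of normal (ULN), confirmed by repeat testing". The second is "ALT or AST > 5 x ULN for more than 2 weeks if new compared to Baseline, confirmed by repeat testing". The third pairs ALT or AST above 3 x ULN with raised bilirubin or INR, and the fourth pairs it with symptoms, rash or eosinophilia. Both of these also need a repeat test. The events "must be reported by the site when it becomes aware of the ECI".

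**Sampling.** Protocol 14.7 and Table 2 schedule safety labs at Screening and TOC only. Further draws are ad hoc: "If indicated, these may be done more frequently as follow up to a laboratory abnormality".

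**Visit rule.** SAP 10.4 opens by naming efficacy and safety endpoints together, and ends: "Unscheduled visit assessments will be displayed in by-subject listings, without being included in the summaries". The exception is "Unscheduled visits from subjects who attended the TOC visit late will be included if within the analysis window", the window being study days 8 to 13. Within it, "If more than one evaluation is assigned to this window, the evaluation closed to study day 10 will be used for the analysis".

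**Lab analysis.** SAP 11.10.2 provides descriptive statistics of values and changes, a listing of out-of-range results, and shift tables. The shift tables use three classes: values below range, "values within the laboratory reference range (normal) or above the laboratory range (high"). Neither SAP 11.10 nor Protocol 18.8.2 mentions events of clinical interest.

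**The concern.** The protocol singles out one organ-specific risk, defines it by multiples of ULN and requires confirmation by a second test. The lab analysis has no multiples of ULN, and its visit rule normally keeps the second test out of the summaries. A value first seen at an unscheduled visit that is not a late TOC visit enters no lab summary at all.

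Safety of the different dose levels and regimens is a secondary objective (Protocol 8.2), and safety laboratory tests are a named secondary endpoint (Protocol 9.2). At stake is whether the five SCY-078 regimens can be compared on this risk from a table, or only by reading individual listings.

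**Working it through.** The plan has no figure to reproduce. Protocol 18.1 and SAP 6 state that no formal sample size calculation was made, and 6 arms x 30 = 180 is arithmetic only. The check is mainly a reading of the rules against each other.

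**1. Scheduled post-dose lab draws.** Table 2 marks safety labs at Screening and TOC, and none at Day 3 or follow-up. That leaves one scheduled post-dose draw, so a confirmatory repeat is normally unscheduled.

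**2. What the TOC window can hold.** The protocol window is Day 10 ± 2, that is Days 8 to 12; the SAP analysis window is study days 8 to 13. One evaluation per subject is used. A first value and its repeat therefore cannot both enter the TOC summary, whichever of the two is used.

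**3. The more-than-2-weeks criterion.** If the rise is first found at TOC, the criterion is met only after day 8 + 14 = 22 at the earliest, or day 13 + 14 = 27 at the latest. Both lie beyond day 13.

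**4. The four criteria against the lab summaries.**

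| Protocol 16.3 criterion | Can the lab summaries identify it? |
|---|---|
| ALT/AST > 8 x ULN, repeated | No: no ULN category and no pairing with the repeat |
| > 5 x ULN for more than 2 weeks, repeated | No: as above, and it completes outside the window |
| > 3 x ULN with bilirubin > 2 x ULN or INR > 1.5, repeated | No: no within-subject combination; INR is not in the Protocol 14.7 panel |
| > 3 x ULN with symptoms, rash or eosinophilia, repeated | No: no link between lab values and symptoms |

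**5. Three cases under the stated rules.**
- *ALT 10 x ULN at an on-time TOC, confirmed by a later repeat.* The TOC value enters the descriptive statistics, where it may be the arm's maximum, and the high shift cell. The repeat is only listed.
- *ALT 1.1 x ULN at TOC.* It falls in the same shift cell as the first case, though the arm's maximum would differ.
- *A raised ALT first found at an unscheduled visit after day 13.* It is listed only and enters no lab summary.

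**6. Context, with assumed rates.** The documents state no expected rate. The chance of at least one case in an arm of n = 30 is 1 − (1 − p)^30:
- p = 0.5%: 1 − 0.995^30 = 14.0%
- p = 1%: 1 − 0.99^30 = 26.0%
- p = 2%: 1 − 0.98^30 = 45.5%
- p = 5%: 1 − 0.95^30 = 78.5%

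Over this range, an arm may have no case or at least one. These figures are not a forecast.

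**The case against.** The strongest reply is that hepatic events have other routes into the report.

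- **Adverse events.** Protocol 16.1 makes any lab abnormality that the investigator judges clinically significant an AE. SAP 11.10.1 tabulates treatment-emergent AEs by treatment from the date of onset or worsening, so the visit rule does not remove them. This stands. A reader might infer that these events never reach any by-arm table; the documents do not support that. The route is only a partial substitute. It depends on judgement, and Protocol 16.3 does not say that such an event is automatically an AE. Protocol 16.7 grades severity by effect on daily activities, so a symptom-free rise could be graded mild. No event-of-interest flag or ULN multiple is specified for the AE tables.
- **Maximum values.** SAP 10.1 includes the maximum in descriptive statistics, so it would be wrong to say that labs are reported only as low, normal or high. That stands too, but a maximum is not a count of subjects, and it shows neither confirmation nor a concurrent bilirubin rise.
- **Nearest-to-Day-10 rule.** A reader might infer that a lower repeat nearer Day 10 displaces a high TOC value. The text does not support this: a confirmatory repeat is not a late TOC visit, so an on-time TOC value stays in the summary.
- **Consistency with the protocol.** Protocol 18.8.2 asks for values, changes and shifts against the reference range, and the SAP delivers them. The events are a site-reporting duty and are not named as an endpoint. So there is no contradiction, and in a study of about 180 subjects listings can be read directly. They still give no rate by arm.
- **Unseen table list.** SAP section 15 is only a heading in the available text, so an event table there cannot be ruled out. Unless it were exempted, such a table would conflict with the SAP 10.4 rule.

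**Conclusion.** The point holds, limited to the lab summaries and to the lack of a labelled count. Under the visible text, none of the four criteria can be identified from the lab summaries, and values first found at unscheduled visits other than late TOC visits are absent from them.

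No numerical effect can be given. A reader might express the loss as an arm's rate falling from 1/30 to 0/30, but that assumes the event reaches no by-arm table, and the AE route can count it. With no stated event rate, that contrast does not estimate the effect.

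The conclusion assumes that repeats are normally drawn outside a late TOC visit and that SAP section 15 contains no event table. It is a cheap improvement to a named secondary safety endpoint and should be made before unblinding; it does not affect the primary analysis.

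**What to change.** 1. **SAP 10.4:** limit the exclusion of unscheduled assessments to efficacy endpoints and by-visit descriptive statistics.
2. **SAP 11.10.2, worst-value table:** by arm, over all scheduled and unscheduled post-dose results, give the number of subjects with ALT or AST > 3 x, > 5 x and > 8 x ULN, with total bilirubin > 2 x ULN, and with the concurrent combination.
3. **SAP 11.10.2, event count:** by arm, give the number of subjects meeting each Protocol 16.3 criterion.
4. **Stated limits:** say that the INR component and the more-than-2-weeks criterion can be assessed only where extra tests were done, because INR is not in the panel and follow-up has no scheduled labs.

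The cost is SAP wording and one or two tables from data already collected, with no new visit or sample. The drawback is that unscheduled testing may differ between subjects, so worst values are not ascertained equally. The by-visit summaries should therefore stay alongside the new tables.

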11. STATISTICAL EVALUATION

11.1 Subject Disposition

The number and percentage of subjects screened, randomized, included in each analysis population, completing the study, withdrawing from the study (together with the reasons for withdrawal) will be summarized using frequencies and percentages by treatment group. A by-subject listing will be presented for all subject enrollment and disposition. Screen failures and subjects not randomized will be presented in by-subject listings.

The number of days in the study (date of study completion / discontinuation minus date of Day 1 plus 1) will be summarized using descriptive statistics for each treatment group.

Tabulation by study site will be provided.

11.2 Protocol Deviation

Protocol deviations will be logged into the IL2 database and displayed in a by-subject listing. One exception to this is Out of Window (OOW) Visit protocol deviations. A report from DSG eCaseLink will be run at the end of the study to obtain a listing of all OOW Visit protocol deviations.

11.3 Demographic and Baseline Characteristics

Demographics and baseline characteristics will be summarized overall and by treatment for the ITT, PP and Safety populations. The following demographic and baseline variables will be included:

- Age (years)
- Race
- Ethnicity
- Weight (kg)
- Height (cm)
- Body mass index (kg/m²)

11.4 Study Medication and Visit Compliance

For the purpose of blinding, the number and appearance of dosage units will be the same across all treatment groups, as follows:

- Day 1: 5 tablets for the morning dose + 3 tablets and 1 capsule for the evening dose
- Day 2 and Day 3: 2 tablets for the morning dose + 2 tablets for the evening dose

The following parameters of study drug exposure and compliance will be summarized for each treatment group:

- Total number of doses taken, calculated as 6 minus total number of doses missed; if a subject's drug accountability missing, the subject's number of doses taken will be assumed as missing
- Total number of bottles returned
- Total number of tablets/capsules taken, calculated as total number of tablets/capsules dispensed minus total number of tablets/capsules returned; total number of tablets/capsules = 17 (9 on Day 1 plus 4 on Day 2 and Day 3 each)
- Subjects with any non-compliance issue based on investigator's review of subject diary

11.5 Prior and Concomitant Medications

Prior (within the previous 28 days and with stop dates prior to first dose of study drug) and concomitant (ongoing or with stop dates on or after first dose of study drug) medications will be presented for the safety population in a by-subject listing for each treatment group. If the medication is ongoing or the stop year is missing, the medication will be considered as received for the entire duration of the study. Medications will be coded using WHO-DD terminology.

For the determination of prior vs concomitant medications, the following rules regarding the stop date will be applied:

- If only year was recorded, and it is before Baseline, it is a prior medication; if year is same or after Baseline, it is assumed to be a concomitant medication.
- If day is missing, but month and year are before Baseline, it is a prior medication; if month and year are the same as Baseline, it is assumed to be a concomitant medication; if month and year are after Baseline, it is a concomitant medication.
- If start date is after Baseline, it is a concomitant medication regardless.

In addition, prior and concomitant medications will be summarized by treatment, WHO-DD Anatomical-Therapeutic-Chemical (ATC) classification and preferred term (PT).

11.6 Medical History and Concurrent Procedures

Medical history (including previous and ongoing medical conditions) will be coded using MedDRA and presented in a by-subject listing.

11.7 Physical Examination

Abnormal findings of physical examination at Screening and TOC will be presented in a by-subject listing.

11.8 Efficacy Endpoints

11.8.1 Primary Efficacy Endpoint

The primary efficacy endpoint is the percentage of subjects with Clinical Cure at the TOC visit.

Clinical Cure is defined as complete resolution of signs and symptoms of vulvovaginal infection without need for further antifungal treatment. Specifically, for complete resolution, any sign or symptom should be absent (score = 0) by the TOC visit. If any sign or symptom is missing, the subject's Clinical Cure status will be considered as missing.

Conversely, Clinical Failure is defined as no response to therapy or incomplete resolution of signs and symptoms or need for additional vulvovaginal or systemic antifungal therapy. If the subject receives or self-administers topical drug therapy for the treatment of vulvovaginal irritation/pruritus such as topical analgesic or corticosteroid after completing treatment with the study drug and before the TOC visit, the subject is considered a clinical failure.

The signs (edema, erythema and excoriation or fissures) and symptoms (itching, burning and irritation) of infection will be assessed by the investigator and the subject, respectively, on the VSS Scale. The VSS Scale is a standardized, predefined scale where each sign and symptom will

be given a numerical rating based on severity (absent = 0; mild = 1; moderate = 2; severe = 3) to calculate a total composite score.

11.8.2 Secondary Efficacy Endpoints

The secondary efficacy endpoints include the following:

- The percentage of subjects with Mycological Eradication (negative fungal culture) at the TOC and FU visit.

Mycological Eradication is defined as a subject with negative culture (no growth) for *Candida* species. Conversely, Mycological Persistence is defined as a subject with positive culture for *Candida* species.

- The percentage of subjects with both Clinical Cure and Mycological Eradication at the TOC visit. If either component assessment is missing, the subject will be considered as missing for this endpoint and imputed as non-responders in the analysis
- The percentage of subjects with both absence of signs and symptoms and Mycological Eradication at the FU visit. If either component assessment is missing, the subject will be considered as missing for this endpoint and imputed as non-responders in the analysis
- The percentage of subjects with Continued Clinical Response at the Follow-up (FU) visit, defined as continued absence of signs and symptoms in subjects who achieved Clinical Cure at the TOC visit
- The time to resolution of signs and symptoms after initiation of study drug, defined as time (days) from first dose of study medication to the first resolution of signs and symptoms. Subjects who discontinued early will be censored at the last available assessment.

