The primary endpoint for the study is clinical cure (complete resolution of signs and symptoms) of the acute symptomatic episode at the test-of-cure (TOC) visit on Day 10 (± 2), which is in line with current regulatory guidance for this condition.⁹ The secondary efficacy endpoints will include mycological eradication (negative fungal culture) at TOC, a composite endpoint of both clinical cure and mycological eradication at the TOC and FU visits, continued clinical response (continued absence of signs and symptoms) at the Follow-up (FU) visit on Day 25 (+4), and time to resolution of signs and symptoms, which are also in line with current guidelines. The safety and tolerability of SCY-078 will also be evaluated as secondary objectives. Other objectives of the study will be to explore the efficacy of SCY-078 based on KOH testing at the TOC visit and based on additional clinical outcomes (clinical response regardless of clinical outcome at TOC) at the FU visit, to explore the prevalence of different *Candida* species, to explore the *in vitro* activity of SCY-078 against baseline *Candida* spp. isolates, to explore clinical and mycological outcomes by *Candida* species, and to evaluate the PK of SCY-078.

Rationale for Study Design

This trial is being conducted as a double-blind, double-dummy study. This design is considered an appropriate design for this indication and phase of investigation, and will use matching SCY-078 and fluconazole placebo to accommodate the differences in the dosing regimens and formulations of SCY-078 and the comparator (fluconazole).

The data generated from this study will provide an initial characterization of the safety and tolerability of SCY-078 in subjects with AVVC, and will provide an initial indication of the most effective dosing regimen with efficacy of SCY-078 in this condition. Results from this study will guide subsequent phases of development for this indication.

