9.2 Secondary Endpoints

Efficacy as measured by:

- The percentage of subjects with mycological eradication (negative fungal culture) at the TOC visit

- The percentage of subjects with both clinical cure and mycological eradication at the TOC and FU visits.
- The percentage of subjects with continued clinical response (continued absence of signs and symptoms) at the Follow-up (FU) visit.
- The time to resolution of signs and symptoms after initiation of study drug

Safety and tolerability as measured by:

- AEs, treatment discontinuations, vital signs, physical examination and safety laboratory tests

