18.7 Efficacy

18.7.1 Efficacy Assessments

The primary efficacy endpoint of the study is the percentage of subjects with clinical cure (complete resolution of signs and symptoms) at the TOC visit. Secondary efficacy endpoints include the percentage of subjects with mycological eradication (negative fungal culture) at the TOC visit, the percentage of subjects with both clinical cure and mycological eradication at the TOC and FU visits, the percentage of subjects with continued clinical

response (continued absence of signs and symptoms) at the FU visit and the time to resolution of signs and symptoms after initiation of study drug. The percentage of subjects with a negative KOH test at the TOC visit, the percentage of subjects who are free of signs and symptoms at the FU visit, the percentage of subjects by *Candida* species infection at Baseline, the percentage of isolates susceptible to SCY-078 and fluconazole, the percentage of subjects with clinical cure (complete resolution of signs and symptoms) at TOC by *Candida* species and the percentage of subjects with mycological eradication (negative fungal culture) at TOC by *Candida* species will be evaluated as exploratory endpoints.

The following treatment outcome definitions will be used for the assessment of efficacy:

Clinical Outcome

- **Clinical cure:** Complete resolution of signs and symptoms of vulvovaginal infection without need for further antifungal treatment. Specifically, for complete resolution, any sign or symptom should be absent (score = 0) by the TOC visit.
- **Clinical failure:** No response to therapy or incomplete resolution of signs and symptoms or need for additional vulvovaginal or systemic antifungal therapy. If the subject receives or self-administers topical drug therapy for the treatment of vulvovaginal irritation/pruritus such as topical analgesic or corticosteroid after completing treatment with the study drug and before the TOC visit, the subject is considered a clinical failure.
- **Continued Clinical Response:** Continued absence of signs and symptoms of vulvovaginal infection at the FU visit in subjects who achieved clinical cure at the TOC visit.
- **Free of Signs and Symptoms:** Absence of signs and symptoms of vulvovaginal infection at the FU visit.
- **Mycological Outcome**
- **Mycological eradication:** A subject with negative culture (no growth) for *Candida* species.
- **Mycological persistence:** A subject with a positive culture for *Candida* species.

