11.9.2 Secondary Efficacy Analyses

The secondary efficacy analyses will be conducted using the mITT, ITT and PP populations.

Binary efficacy endpoints (mycological eradication, composite clinical cure and mycological eradication, and continued clinical response at FU) will be analyzed using the same methods/tests as described for the primary efficacy endpoint.

Time to resolution of signs and symptoms after initiation of study drug will be analyzed using Kaplan-Meier methods. Pairwise treatment comparisons of SCY-078 vs. fluconazole will be performed using log-rank test.

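### The SAP's FU composite scores visit status only and omits the no-further-antifungal condition that clinical cure carries in both documents

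*SAP*

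**What the plan says.** Protocol 9.2 names one secondary composite: "both clinical cure and mycological eradication at the TOC and FU visits". Protocol 18.7.1 defines clinical cure as "Complete resolution of signs and symptoms of vulvovaginal infection without need for further antifungal treatment". It then ties the score-of-zero requirement to TOC, and it gives no separate FU version of clinical cure. SAP 11.8.1 keeps the antifungal condition in its own definition of Clinical Cure and lists "need for additional vulvovaginal or systemic antifungal therapy" among the grounds for Clinical Failure.

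SAP 11.8.2 splits the composite by visit. At TOC the clinical half is Clinical Cure. At FU the requirement is "both absence of signs and symptoms and Mycological Eradication at the FU visit", with nothing about other antifungals.

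Protocol 18.7.1 has a separate outcome, Free of Signs and Symptoms: "absence of signs and symptoms of vulvovaginal infection at the FU visit". It is listed as exploratory in Protocol 9.3 and SAP 11.8.3. Protocol 7.2 describes the additional FU outcomes as "clinical response regardless of clinical outcome at TOC".

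SAP section 12 says that the SAP follows the protocol with no significant change, and it lists none.

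**The concern.** The clinical half of the FU composite has the content of the exploratory Free of Signs and Symptoms outcome, not of clinical cure. The difference matters for one kind of subject: she takes a non-study antifungal at some point before FU and is symptom-free and culture-negative when FU comes. The SAP counts her as an FU success of the assigned regimen, although another drug may have produced the result.

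The study's primary objective is to compare regimens and recommend a dose. Arms with more TOC failures contain more women who might turn to another antifungal, so this scoring would tend to narrow differences between arms on the endpoint that speaks to durable response.

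**Working it through.** The plan states no figure to reproduce here: there is no powered sample size, only 6 × 30 = 180, which is consistent. The check is a comparison of texts, followed by a sizing.

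**1. Are the two terms synonyms?** No. SAP 11.8.1 includes the antifungal condition in Clinical Cure, and SAP 11.8.2 uses that term at TOC but not at FU.

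**2. Does another SAP rule restore the condition at FU?**
- SAP section 8: "subjects who have a missing value at the TOC visit or FU visit will be assigned as treatment failures". This covers missing values only, not antifungal use.
- SAP section 7: interfering concomitant medication is an example of a major deviation, which removes a subject from PP. It does not affect mITT (primary) or ITT.
- SAP 11.9.2 refers to the endpoint in shorthand, "composite clinical cure and mycological eradication, and continued clinical response at FU", and adds no scoring rule.

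**3. Trace two subjects who are clear and culture-negative at FU.**

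| Subject | SAP 11.8.2, FU composite | Protocol, response at both visits | Protocol, each visit separately |
|---|---|---|---|
| Clinical failure at TOC, then takes a non-study antifungal | Responder | Non-responder (failed at TOC) | Non-responder, if the antifungal condition is carried to FU |
| TOC responder, relapses, then takes a non-study antifungal | Responder | Non-responder, on the same inference | Non-responder, on the same inference |

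**4. Size per subject.** One subject moves an arm's rate by 100/n points. At n = 30 (Protocol 18.1) this is 100/30 = 3.3. mITT arms will be smaller if some baseline cultures are negative; at an assumed n of 27, 24 or 20 the step is 3.7, 4.2 or 5.0.

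**5. Illustration. Every rate here is assumed.** Let p be the TOC composite response (0.75 and 0.55 in two arms), h = 0.85 the share of responders kept to FU, u = 0.10 clearance among TOC non-responders without another antifungal, k = 0.60 clearance with one, and r the share of TOC non-responders who take one.

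- Current rule: p·h + (1−p)·[r·k + (1−r)·u]
- Use scored as non-response: p·h + (1−p)·(1−r)·u

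For r = 0.10, the current rule gives 0.6375 + 0.25 × (0.06 + 0.09) = 67.5% and 0.4675 + 0.45 × 0.15 = 53.5%, a difference of 14.0 points. With use scored as non-response, the rates are 0.6375 + 0.25 × 0.09 = 66.0% and 0.4675 + 0.45 × 0.09 = 50.8%, a difference of 15.2 points.

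| r | Current rule | Use = non-response | Gap between rules, points | Extra responders of 30, weaker arm: 30(1−p)·r·k |
|---|---|---|---|---|
| 0.05 | 66.9 vs 52.4, diff. 14.5 | 66.1 vs 51.0, diff. 15.1 | 0.6 | 0.4 |
| 0.10 | 67.5 vs 53.5, diff. 14.0 | 66.0 vs 50.8, diff. 15.2 | 1.2 | 0.8 |
| 0.25 | 69.4 vs 56.9, diff. 12.5 | 65.6 vs 50.1, diff. 15.5 | 3.0 | 2.0 |

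Varying k from 0.5 to 0.7 gives current-rule differences of 14.6 to 14.4, 14.2 to 13.8 and 13.0 to 12.0. If relapsing TOC responders take another antifungal at the same rates, p·(1−h)·r·k is added to the current rule and the differences become 14.6, 14.2 and about 13.

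**The case against.** The strongest reply is that the SAP filled a gap. Several protocol sections gloss clinical cure as resolution of signs and symptoms with no antifungal clause, the full definition is anchored to TOC, and the FU ratings are described as the means of judging clinical outcome. This stands in part: the SAP had to write something for FU, and carrying the antifungal condition to FU on the per-visit reading is an inference. A reader might infer that the SAP overrode an explicit FU definition of cure; there is none to override. But only the score-of-zero sentence carries the TOC anchor, so moving the assessment to FU did not require dropping the antifungal condition.

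Non-study antifungals are prohibited (Protocol 13.2 and Appendix A), so use may be rare. That limits the size but does not settle the scoring, and Protocol 13.1 provides for recording such use after TOC. The illustration may also overstate exposure: it applies r to every TOC composite non-responder, including clinically cured, culture-positive women with no symptoms to treat.

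Two further inferences are too strong. One is that the FU result will be reported under a false label: SAP 11.9.2 is shorthand for both composites, and the table titles cannot be seen. The other is that section 12 is untrue: it denies significant change, not all change, and whether this change is significant is a matter of judgement. Noting it there is still good practice.

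**Conclusion.** The concern holds in a limited form. The FU composite in SAP 11.8.2 omits a condition that both documents attach to clinical cure, and no other rule restores it in mITT or ITT. The scoring that results conflicts with the most natural reading of Protocol 9.2 and 18.7.1. The wording difference is certain; applying the condition at FU is a strong inference.

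The size is 3.3 points per affected subject in an arm of 30. The number of such subjects is unknown. On the assumed rates, the between-arm difference shifts by about 1 point or less at 5% to 10% use and by 3 points at 25%.

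A reader might infer that the rule could decide a comparison. Counts can be chosen to show this: 21/30 versus 12/30 gives Fisher p = 0.037, and one more comparator responder gives p = 0.067. But those counts are invented and put the extra responder in one arm only. The study is exploratory and not powered for formal comparisons, and no stated dose-selection rule uses this endpoint.

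The primary endpoint and the TOC composite are unaffected, and PP is a partial check. Nor do the documents support extending the point to Mycological Eradication or Continued Clinical Response, whose definitions follow the protocol's own.

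**What to change.** Before unblinding:

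- In SAP 11.8.2, score a subject as a non-responder for the FU composite if the eCRF records any non-study vulvovaginal or systemic antifungal between first dose and the FU assessment, or the need for one. Add no limit on indication, because the protocol's failure definition has none.
- Keep the current version as a sensitivity analysis, labelled as absence of signs and symptoms plus negative culture.
- Note the FU wording of the composite in SAP section 12.
- Leave Free of Signs and Symptoms as plain FU status. Applying the same rule to Mycological Eradication and Continued Clinical Response is optional; it would depart from the protocol's definitions and should be listed in section 12 if adopted.

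The cost is one scoring rule, one derived flag and a line in section 12. Protocol 13.1 already provides for recording antifungal use through FU. The documents name no separate field for judged need, so in practice the flag will rest mainly on recorded use. FU composite rates may be slightly lower, and a subject given an antifungal for another indication would count as a non-responder.
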